7.6.2.2. Reporting Other Special Situations

Site personnel must record all other special situations data in the eCRF database and from there transmit the special situations information to Gilead GLPS within 24 hours of the investigator's knowledge of the event. Detailed instructions can be found in the eCRF completion guidelines. All special situations data will be recorded in the eCRF database within the timelines outlined in the eCRF completion guidelines. These reports must consist of situations that involve study drug and/or Gilead CMs, but do not apply to non-Gilead CMs.

If it is not possible to record and submit the special situations information electronically, because the eCRF database cannot be accessed or is not available (including at study start), record the information on the paper special situations report form and submit by e-mail or fax within 24 hours of the investigator's knowledge of the event to Gilead GLPS. Gilead GLPS contact information is as follows:

Email: **PPD** and Fax: **PPD**

As soon as it is possible to do so, any special situations reported via paper must be transcribed into the eCRF database according to instructions in the eCRF completion guidelines. If any special situations have been reported via a paper form because the eCRF database has been locked, no further action is necessary.

Special situation reports involving a Gilead concomitant therapy (not considered study drug), that occurs after the subject first consents to participate in the study (ie, signing the informed consent) and throughout the duration of the study, including the posttreatment follow-up period, must be reported to Gilead GLPS utilizing the paper SSR form.

Special situations involving non-Gilead CMs do not need to be reported on the SSR form; however, for special situations that result in AEs due to a non-Gilead CM, the AE should be reported on the AE form.

Any inappropriate use of CMs prohibited by this protocol should not be reported as "misuse," but may be more appropriately documented as a protocol deviation.

Refer to Section [7.3](#) and the CRF/eCRF completion guidelines for full instructions on the mechanism of special situations reporting.

All clinical sequelae in relation to these SSRs will be reported as AEs or SAEs at the same time using the AE CRF/eCRF and/or the SAE report form. Details of the symptoms and signs, clinical management, and outcome will be reported, when available.

8. STATISTICAL CONSIDERATIONS

Details will be provided in the Statistical Analysis Plan (SAP).

8.1. Analysis Objectives and Endpoints

8.1.1. Analysis Objectives

The **primary objective** of this study is as follows:

- To assess the safety and tolerability of escalating doses of CILO in subjects with PSC and compensated cirrhosis

CCI

8.1.2. Primary Endpoint

The primary endpoint is the safety and tolerability of CILO in subjects with PSC and cirrhosis. The safety and tolerability of CILO will be evaluated by examining treatment-emergent adverse events (TEAEs), including SAEs, clinical laboratory tests, and vital signs assessments at various time points during the study.

CCI

█

█

█

8.2. Analysis Conventions

8.2.1. Analysis Sets

8.2.1.1. Efficacy

The primary analysis set for efficacy analyses will be the Safety Analysis Set, which includes all subjects who were enrolled into the study and received at least 1 dose of study drug.

8.2.1.2. Safety

The primary analysis set for safety analyses will include all subjects who received at least 1 dose of study drug.

CCI

█

█

█

█

█

█

█

█

█

█

█

█

█

█

CCI

8.2.1.5. Biomarkers

The Biomarker Analysis Set will include data from subjects in the Safety Analysis Set who have the necessary baseline and on-study measurements to provide interpretable results for the specific parameters of interest.

8.2.2. Data Handling Conventions

Missing data can have an impact on the interpretation of the study data. In general, values for missing data will not be imputed.

Where appropriate, safety data for subjects that did not complete the study will be included in summary statistics. For example, if a subject received study medication, the subject will be included in a summary of AEs according to the treatment received; otherwise, if the subject is not dosed then they will be excluded from the summary. If safety laboratory results for a subject are missing for any reason at a time point, the subject will be excluded from the calculation of summary statistics for that time point. If the subject is missing a predose value, then the subject will be excluded from the calculation of summary statistics for the predose value and the change from predose values.

Values for missing safety laboratory data and vital signs will not be imputed; however, a missing baseline result will be replaced with a screening result, if available. If no pretreatment laboratory value is available, the baseline value will be assumed to be normal (ie, no grade [Grade 0]) for the summary of graded laboratory abnormalities.

[figure not shown]
8.3. Demographic Data and Baseline Characteristics

Demographic and baseline measurements will be summarized using standard descriptive methods (n, mean, SD, median, Q1, Q3, minimum, and maximum) by overall. Demographic summaries will include sex, race/ethnicity, and age.

Baseline characteristics summary will include body weight, height, body mass index, and other disease characteristics.

8.4. Efficacy Analysis

The biological activity of CILO will be evaluated using biomarker variables. CCI

oint estimates and 95% CI will be provided if applicable.

For all continuous endpoints, descriptive statistics (n, mean, SD, median, Q1, Q3, minimum, and maximum) will be provided. For categorical variables, descriptive statistics will be calculated with count and percentage of subjects in each category.

8.5. Safety Analysis

All safety data collected on or after the date that CILO was first dispensed up to the date of last dose of CILO plus 30 days will be summarized by overall. Data for the pretreatment and follow-up periods will be included in data listings.

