1.2.8.4. Preliminary Safety Results

Treatment with CILO 100 or 30 mg was generally well tolerated in Study GS-US-428-4025. [Table 1-3](#) presents an overall summary of AEs during the 12-week double-blind phase. A majority of subjects in each treatment group experienced at least 1 AE: CILO 100 mg, 18 of 22 subjects (81.8%); CILO 30 mg, 13 of 20 subjects (65.0%); and placebo, 10 of 10 subjects (100.0%). Most AEs were Grade 1 or 2 in severity. Four subjects discontinued study treatment in the double-blind phase due to AEs: 3 subjects (13.6%) in the CILO 100 mg group (due to acute kidney injury, pruritus, and increased ALP, respectively) and 1 subject (10.0%) in the placebo group (due to increased AST, ALT, and ALP). No deaths were reported during the study.

Table 1-3. GS-US-428-4025: Overall Summary of Treatment-Emergent Adverse Events, Double-Blind Phase (Safety Analysis Set)

| | CILO 100 mg (N = 22) | CILO 30 mg (N = 20) | CILO Pooled (N = 42) | Placebo (N = 10) |
|---|-------------------------------------|------------------------------------|-------------------------------------|-----------------------------|
| AE | 18 (81.8%) | 13 (65.0%) | 31 (73.8%) | 10 (100.0%) |
| AE with grade of 3 or higher | 5 (22.7%) | 3 (15.0%) | 8 (19.0%) | 2 (20.0%) |
| AE with highest grade of 3 | 5 (22.7%) | 3 (15.0%) | 8 (19.0%) | 2 (20.0%) |
| Treatment-related AE | 5 (22.7%) | 5 (25.0%) | 10 (23.8%) | 2 (20.0%) |
| Treatment-related AE with grade of 3 or higher | 1 (4.5%) | 1 (5.0%) | 2 (4.8%) | 1 (10.0%) |
| SAE | 3 (13.6%) | 0 | 3 (7.1%) | 0 |
| Treatment-related SAE | 0 | 0 | 0 | 0 |
| AE Leading to Premature Discontinuation of Study Drug | 3 (13.6%) | 0 | 3 (7.1%) | 1 (10.0%) |
| Death during the Study | 0 | 0 | 0 | 0 |

Adverse events were coded according to MedDRA Version 20.1. Severity grades were defined by the CTCAE Version 4.03. Treatment emergent events of the Double Blind Phase began on or after the study drug start date of the Double Blind Phase up to 30 days after permanent discontinuation of study drug in the Double Blind Phase (and before the first dose date in the OLE Phase), or led to premature study drug discontinuation. Death includes any death that occurred during the study.

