1.2.8.6. Serious Adverse Events

Serious AEs were reported in 3 subjects during the double-blind phase, all in the CILO 100 mg group. No SAEs were reported in subjects in the CILO 30 mg group or placebo group. The SAEs were Grade 3 rib fracture (1 subject), Grade 3 acute kidney injury (1 subject), and Grade 3 diarrhea and dehydration (1 subject). None of these events were considered related to study drug; the event of Grade 3 acute kidney injury resulted in premature discontinuation of study drug.

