1.4. Rationale for Dose Selection of CILO

In this study we aim to evaluate the safety and tolerability of escalating daily doses of CILO from 30 to 100 mg once daily in a PSC population with compensated cirrhosis.

A dose of CILO 100 mg daily provided greater therapeutic benefit than a dose of CILO 30 mg in a Phase 2 study in subjects with PSC without cirrhosis (Study GS-US-428-4025). Subjects with compensated cirrhosis are expected to have approximately 1.8-fold higher CILO plasma exposure compared to those without cirrhosis (GS-US-402-3885; Section [1.2.6](#)). CILO is a hepatic OATP substrate, and the higher CILO plasma exposure observed in subjects with compensated cirrhosis is attributable to decreases in hepatic uptake by OATP, and not expected to alter the hepatic exposure of CILO. Thus, a similar dose of CILO 100 mg is expected to be needed for efficacy in subjects with PSC and compensated cirrhosis. Adequate exposure margins (5- to 11-fold relative to preclinical NOAEL exposures) are expected after 100 mg CILO administration in subjects with PSC and compensated cirrhosis.

The current study is designed to assess the safety of increasing daily doses of CILO from 30 to 100 mg daily in subjects with PSC and compensated cirrhosis. The starting dose, CILO 30 mg once daily, was well tolerated following 12 weeks of treatment in subjects with compensated cirrhosis due to NASH (GS-US-384-3914) and conferred improvements in liver biochemistry (eg, GGT) and markers of cholestasis (eg, C4) in patients with noncirrhotic PSC (GS-US-428-4025). After 4 weeks of dosing with CILO 30 mg, the dose will escalate to 60 mg and then to 100 mg over 4-week intervals, to evaluate the safety, tolerability and improvements in ALP and other liver biochemistry tests at each dose level in subjects with PSC and compensated cirrhosis.

Dosing of CILO in this study will be without regard to food based on PK, PD, safety and efficacy data from Phase 1 studies in healthy subjects and subjects with hepatic impairment (GS-US-402-1851, GS-US-454-4315, and GS-US-402-3885) and Phase 2 studies in subjects with NASH with or without cirrhosis (GS-US-402-1852 and GS-US-384-3914).

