8.5.1. Extent of Exposure

Data for a subject's extent of exposure to CILO will be generated from the study drug administration eCRF. Exposure data will be summarized by overall.

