8.5.3. Laboratory Evaluations

Selected laboratory data will be summarized (n, mean, SD, median, Q1, Q3, minimum, and maximum) by study visit along with the corresponding change from baseline values.

Graded laboratory abnormalities will be defined using the grading scheme in the CTCAE Version 5.0 (see [Appendix 3](#)). Grading of laboratory abnormalities for analysis purposes will be performed by the central laboratory.

Incidence of treatment-emergent laboratory abnormalities, defined as values that increase at least 1 toxicity grade from baseline at any time from baseline up to and including the date of last dose of study drug plus 30 days will be summarized by overall. If baseline data are missing, then any graded abnormality (ie, at least a Grade 1) will be considered treatment emergent.

Laboratory abnormalities that occur before the first dose of study drug or after the subject has been discontinued from treatment for at least 30 days will be included in a data listing.

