7.1.6. Summaries of Adverse Events and Deaths

Treatment-emergent AEs will be summarized based on the Safety Analysis Set.

A brief, high-level summary of the number and percentage of subjects who experienced at least 1 TEAE in the categories described below will be provided. All deaths observed in the study will also be included in this summary.

- TEAE
- TEAEs with Grade 2 or higher
- TEAEs with Grade 3 or higher
- TE treatment-related AEs
- TE treatment-related AEs with Grade 2 or higher
- TE treatment-related AEs with Grade 3 or higher
- TE SAEs
- TE treatment-related SAEs
- TEAEs leading to premature discontinuation of study drug
- TEAEs leading to temporary interruption of study drug
- Death

The number and percentage of subjects who experienced at least 1 TEAE will be provided and summarized by SOC and PT for the AE categories described below:

- TEAE
- TEAEs with Grade 2 or higher
- TE treatment-related AEs
- TE SAEs
- TEAEs leading to premature discontinuation of study drug
- TEAEs leading to temporary interruption of study drug

Summaries of all TEAEs by PT only, and by SOC, PT, and maximum severity will also be provided.

Multiple events will be counted only once per subject in each summary. Adverse events will be summarized and listed first in alphabetic order of SOC (if applicable), and then by PT in descending order of total frequency within each SOC. For summaries by severity grade, the most severe grade will be used for those AEs that occurred more than once in an individual subject during the study.

In addition, data listings will be provided for the following:

- All AEs, indicating whether the event is treatment emergent
- All TEAEs with severity of Grade 2 or higher
- All SAEs
- All deaths
- All AEs leading to premature discontinuation of study drug
- All AEs leading to temporary interruption of study drug

7.2. **Laboratory Evaluations**

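### Primary safety tables pool the 30, 60 and 100 mg stages into one overall column, although the stages exist to assess safety at each dose

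*Protocol*

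**What the plan says.** The primary objective (Protocol Sections 2 and 8.1.1) is the safety and tolerability of escalating doses. Section 1.4 gives the purpose of the 30, 60 and 100 mg stages: "to evaluate the safety, tolerability and improvements in ALP and other liver biochemistry tests at each dose level".

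The protocol's analysis section reports one group:

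- Section 8.5, safety data: "up to the date of last dose of CILO plus 30 days will be summarized by overall".
- Section 8.5.1: "Exposure data will be summarized by overall".
- Section 8.5.3, treatment-emergent laboratory abnormalities up to "last dose of study drug plus 30 days will be summarized by overall".

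The visible SAP keeps that structure:

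- **Adverse events (7.1.5, 7.1.6).** There is one window, from first dose to 30 days after stopping. Each subject counts once per summary. In severity tables, "the most severe grade will be used for those AEs that occurred more than once in an individual subject during the study".
- **Graded laboratory results (7.2.2.2) and liver criteria (7.2.3).** Subjects are classified by their worst value after baseline.
- **Numeric laboratory summaries (7.2.1).** The by-visit tables promised in Protocol Section 8.5.3 are dropped.
- **Exposure (4.2.1) and adherence (4.2.2.1).** Total duration, and one total column.
- **Disposition (4.1).** One row gives the dose level at a PI-approved interruption. Completion and reasons for stopping are counted, but not by dose.

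**The concern.** The stages were built to learn about each dose, and the tables that report the primary endpoint remove dose. A reader of the adverse event table could not tell whether events began at 30, 60 or 100 mg. The overall denominator also includes subjects who never took the higher doses, since only those judged to tolerate a dose escalate (Protocol Section 3.1).

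This matters most for the upper stages. Section 1.4 already reports that 30 mg "was well tolerated following 12 weeks of treatment in subjects with compensated cirrhosis due to NASH", so much of what is new concerns 60 and 100 mg, which a pooled column cannot isolate. If someone later rebuilds by-dose figures from the listings, the rule for assigning events to a dose will have been chosen after the data were seen.

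**Working it through.** The plan contains no power calculation or target rate, so there is no planned figure to reproduce. The check compares the texts and then shows the size of what is lost. Intervals are exact (Clopper-Pearson) 95%.

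**1. Is there a dose split anywhere in the visible text?** The SAP passages listed above define no dose columns. Protocol Section 8.2.2 puts dosed subjects in adverse event summaries by treatment received, but as a missing-data example, with no rule for a subject who received up to three doses. The dose at interruption (SAP 4.1) is the only table item that names a dose. Categorical laboratory data are shown by scheduled visit (SAP 7.2.2.2). For uninterrupted subjects the Week 4, 8 and 12 samples fall close to the end of each stage: drug is held until blood is drawn (Protocol 6.4.1), the record nearest the nominal day is used (SAP 3.7.3), and study day is reset after an interruption (SAP 3.7.1). That gives an indirect dose link for those data, but not for adverse events or worst-grade tables.

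**2. The earlier PSC study** (Protocol Table 1-3 and Section 1.2.8.6). "Serious AEs were reported in 3 subjects during the double-blind phase, all in the CILO 100 mg group".

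| Column | SAEs | Rate | 95% interval |
|---|---|---|---|
| 100 mg | 3/22 | 13.6% | 2.9 to 34.9 |
| 30 mg | 0/20 | 0% | 0 to 16.8 |
| Pooled cilofexor | 3/42 | 7.1% | 1.5 to 19.5 |

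Discontinuations for adverse events on cilofexor give the same figures. The pooled 7.1% would be identical had all three subjects been on 30 mg.

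**3. Dilution in this trial.** Suppose events occur only at 100 mg, at rate p, and a fraction f of subjects reach that dose. The overall column then prints p × f. With p = 30% (assumed):

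- f = 50%: 0.30 × 0.5 = 15%
- f = 70%: 0.30 × 0.7 = 21%
- f = 90%: 0.30 × 0.9 = 27%

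**4. In whole subjects.** About 20 were planned (Protocol 4.1). Enrolment stopped early (SAP 1), and the final number is not given. With 70% reaching 100 mg (assumed):

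| N | At 100 mg | Overall |
|---|---|---|
| 10 | 2/7 = 28.6% (3.7 to 71.0) | 2/10 = 20.0% (2.5 to 55.6) |
| 20 | 4/14 = 28.6% (8.4 to 58.1) | 4/20 = 20.0% (5.7 to 43.7) |

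**5. Why an assignment rule is needed.** If follow-up after the last dose is credited to the last dose, a subject who completes treatment has 28 + 30 = 58 attributable days at 100 mg against 28 at each lower dose, a ratio of 58/28 = 2.07. The laboratory schedule is also sensitive to the rule. Scheduled on-treatment samples fall at nominal Days 8, 29, 57 and 85. By last dose taken before the sample, they split 2/1/1 across 30/60/100 mg. By dose on the sampling date, they split 1/1/2, which moves the Week 4 sample to 60 mg and the Week 8 sample to 100 mg.

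**6. Adherence does not fill the gap.** It counts tablets regardless of strength, against 28 + 2 × 28 + 28 = 112. A subject who stops after the 60 mg stage has 84/112 = 75% of the tablets but (28 × 30 + 28 × 60)/(28 × 190) = 47.4% of the planned milligrams.

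**The case against.** The strongest reply is that the trial tests a titration regimen. The phrase about each dose level sits in a rationale paragraph, while the endpoint in Section 8.1.2 is the safety of cilofexor, which an overall column does describe. With about 20 subjects planned, early termination and full listings, each event's dose can be read by hand. By-dose rates such as 2/7 could invite a dose-response reading that the design cannot support. The earlier study is also an imperfect parallel: its arms were randomized and concurrent, none of its serious events was judged related to drug, and 3/22 against 0/20 gives a two-sided Fisher p of 0.23. Finally, the 30 mg experience in cirrhosis comes from NASH, so 30 mg in PSC cirrhosis is not settled either.

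Much of this stands as a limit on interpretation. By-dose figures would be descriptive only, the earlier study illustrates lost information and does not establish a dose effect, and a small final sample justifies a lighter remedy. None of it removes the mismatch. The stated purpose names each dose level, the primary tables cannot show it, and reading the listings by hand still needs a rule that the visible plan does not contain.

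**Conclusion.** The concern holds. As written, the primary safety tables cannot show the dose at which events arose. Pooling would have shown 13.6% and 0% as 7.1% in the sponsor's earlier study; under the assumptions above it would show 30% as 15% to 27% here. Nothing in the plan is invalidated, so this is a point that should be fixed, at low cost.

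The conclusion covers the visible text. SAP Sections 6, 8 and 9 are blacked out, and Appendix 3 and the table shells are not in the supplied text, so by-visit liver tests, itch scores, pharmacokinetics and pharmacodynamics are outside it. SAP 4.1 refers to columns without naming them. The sections where dose columns for adverse events, graded laboratory results and exposure would be defined are visible, and they define none.

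**What to change.** Keep the overall column and add descriptive 30, 60 and 100 mg columns:

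1. **Adverse events by dose at onset**: all, related, and those leading to interruption or discontinuation. The denominator is subjects who took at least one dose at that level, with the worst grade taken within dose. State a rule for onset on the day a new dose starts, for example assignment to the new dose unless a recorded time shows otherwise.
2. **Graded laboratory results and the SAP 7.2.3 liver criteria by the last dose level taken before the sample**, so that Week 4 and Week 8 samples count to 30 and 60 mg. A Week 12 sample on the last dosing day or the day after stays with that stage. The denominator is subjects with a result on that dose.
3. **A separate off-drug column**, labelled with the last dose taken, for events and results during an interruption or later in the 30 days after the last dose.
4. **One tolerability table per dose**: entered, completed 28 consecutive days, interrupted, stopped, not escalated.
5. **Exposure in days per dose.**

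If the final number is very small, by-dose counts and a dose-at-onset field in the adverse event listing are enough.

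The cost is SAP wording, one derived variable and a few columns. The data exist: events are already summarized by onset date (Protocol 8.5.2), dose regimen with start and end dates is required source data (9.1.6), and drug administration is listed by visit (SAP 4.2.2.1). The SAP should say that by-dose results are descriptive, because dose is confounded with time on study, with selection of subjects who tolerated the previous dose, and with possible carry-over, and because scheduled laboratory samples are unequal (2/1/1).

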8.5.1. Extent of Exposure

Data for a subject's extent of exposure to CILO will be generated from the study drug administration eCRF. Exposure data will be summarized by overall.

8.5.2. Adverse Events

Clinical and laboratory AEs will be coded using the Medical Dictionary for Regulatory Activities (MedDRA). System Organ Class (SOC), High-Level Group Term (HLGT), High-Level Term (HLT), Preferred Term (PT), and Lower-Level Term (LLT) will be attached to the clinical database. Adverse event severity will be graded using the CTCAE Version 5.0.

Events will be summarized on the basis of the date of onset for the event. Treatment-emergent AEs are defined as 1 or both of the following:

- Any AEs with an onset date on or after the study drug start date and no later than 30 days after permanent discontinuation of study drug
- Any AEs leading to premature discontinuation of study drug

Summaries (number and percentage of subjects) of TEAEs by SOC and PT will be provided. Treatment-emergent AEs will also be summarized by relationship to study drug and severity. In addition, TEAEs leading to premature discontinuation of study drug and study will be summarized and listed.

All AEs collected during the course of the study will be presented in data listings with a field for treatment-emergent event (yes/no).

